14.8. Safety Analyses

Safety analyses will be performed on the Safety Set, which includes all patients who receive at least 1 dose of ORGN001.

14.8.1. Adverse Events

All AEs arising after signing the ICF will be coded using the Medical Dictionary for Regulatory Activities (MedDRA; Version 22.0 or higher) and displayed in listings.

[REDACTED]

[REDACTED]

[REDACTED]

[REDACTED]

[REDACTED]

[REDACTED]

[REDACTED]

Treatment-emergent adverse events are AEs with onset on or after the first date of ORGN001 administration. Treatment-emergent adverse events will be summarized by System Organ Class (SOC) and Preferred term for all events and those considered at least possibly related (including missing relationship) to ORGN001 by the Investigator, both overall and by severity. Serious TEAEs will be tabulated by SOC and Preferred term.

Summaries will include both the number of patients affected and the number of events. For patient counts in summaries by severity or relationship, if a patient has more than one occurrence of an AE for a specific Preferred Term or SOC, the patient will be counted only once in the most extreme category of severity or relationship observed.

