3. STUDY OBJECTIVES AND ENDPOINTS

3.1. Objectives

Primary:

- To evaluate the safety and efficacy of ORGN001 in neonate, infant, and pediatric patients with MoCD Type A who are either treatment-naïve or who have received compassionate use ORGN001

Secondary:

- To evaluate the effect of ORGN001 on growth and development using age-appropriate assessments
- To evaluate the effect of ORGN001 on pediatric measures of functional ability and activities of daily living

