7.2. Patient Inclusion Criteria

Patients must meet all of the inclusion criteria to be considered eligible for enrollment in this study.

- Male or female neonatal patients (1 to 28 days of age [inclusive] at the time of ORGN001 administration, with day 1 of age corresponding to the day of birth), or infant (29 days to < 2 years of age) or child (2 to 5 years of age [inclusive]) with MoCD Type A, previously untreated with ORGN001 or treated with ORGN001 through the EAP
- In neonates, diagnosis of MoCD Type A, based on:
 - Prenatal genetic diagnosis, or
 - Onset of clinical and/or laboratory signs and symptoms consistent with MoCD Type A (eg, seizures, exaggerated startle response, high-pitched cry, axial hypotonia, limb hypertonia, feeding difficulties, elevated urinary sulfite and/or SSC, elevated xanthine in urine or blood, or low or absent uric acid in the urine or blood) within the first 28 days after birth
- In infants or children, diagnosis of MoCD Type A, based on:

- Confirmed genetic diagnosis (genetic confirmation of the diagnosis of MoCD Type A may be obtained after initiation of ORGN001 therapy in certain cases), biochemical profile, and clinical presentation consistent with MoCD Type A
- Parent or legal guardian must have signed the ICF prior to any study procedures being performed

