8.2. Prior and Concomitant Medications and Procedures

Prior medications, defined as any drug or substance taken by the patient within 28 days prior to the time the parent or legal guardian signs the ICF until the first ORGN001 dose, and concomitant medications, defined as any drug or substance taken by the patient after the first ORGN001 dose until completion of the last study visit, will be recorded on the patient's CRF.

Prior procedures, defined as any therapeutic intervention (eg, surgery/biopsy, physical therapy) performed within 28 days prior to the time the parent or legal guardian signs the ICF until the first ORGN001 dose (not to exclude the collection of data on relevant procedures as part of Medical History conducted more than 28 days prior to consent), and concomitant procedures, defined as any therapeutic intervention (eg, surgery/biopsy and physical therapy) performed after the first ORGN001 dose drug until completion of the last study visit, will be recorded on the patient's CRF. If possible, elective surgical procedures should not be performed during the initial 12-month study period.

[figure not shown]
ORGN001 is not an inhibitor of cytochrome P450 (CYP450) enzymes *in vitro*; therefore, concurrent administration of ORGN001 is unlikely to affect systemic exposure of other CYP substrates. CYP isoforms responsible for biotransformation of ORGN001 are unknown.

Changes in a patient's anticonvulsants, including the reason for the change, will be recorded. Adverse events related to administration of these therapies or procedures must be documented on the appropriate CRF.

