13.5. Adverse and Serious Adverse Events

13.5.1. Definition of an Adverse Event

An AE is defined as any unfavorable or unintended sign (eg, including an abnormal laboratory finding), symptom, or disease temporally associated with the use of a medicinal product or procedure, whether or not considered related to the medicinal product or procedure, that occurs during the study.

Exacerbations of a chronic or intermittent pre-existing condition, including either an increase in frequency and/or intensity of the condition, are all to be considered AEs.

Abnormal test findings may be considered AEs. If an abnormal laboratory value is identified, Investigators are strongly encouraged to report a diagnosis, or a sign or symptom rather than an isolated abnormal test value. An abnormal test finding should be documented as an AE if any of the following conditions are met:

- Is associated with a sign or symptom
- Requires additional diagnostic testing (repeat tests are not considered additional testing)
- Requires a medical or surgical intervention
- Leads to a change in study dosing outside of the protocol-defined dosing or discontinuation from the study
- Or does not meet any of the defined conditions, but the Investigator or Sponsor considers the result as clinically significant or meeting the definition of an AE.

This definition also includes signs or symptoms resulting from misuse or abuse of the product from drug overdose, drug withdrawal, medication error, as well as outside what is foreseen in the protocol, such as drug interactions and extravasation.

An AE does not include the following:

- Medical or surgical procedures (eg, surgery, endoscopies, tooth extraction, and transfusion). The condition that leads to the procedure is the AE (eg, laparoscopic cholecystectomy is the procedure or treatment for an SAE of necrotic gall bladder).
- Pre-existing diseases or conditions present or detected prior to the Screening/Baseline evaluation that do not worsen
- Situations where an untoward medical occurrence has not occurred (eg, hospitalization for elective surgery, social, and/or convenience admissions)

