13.5.2. Detection of Adverse Events

The Investigator is responsible for detecting, assessing, documenting, and reporting all AEs. All serious and nonserious AE information will be collected from the time informed consent is signed until study completion.

Adverse events reported by the patient and/or parent or legal guardian, and/or identified in response to an open-ended question from study personnel, or revealed by observation, physical examination, or other study procedures, must be collected and recorded as described in [Section 13.5.3](#).

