14.2. Analysis Populations

Safety analyses will be performed on a Safety Set, defined as all patients who received at least 1 infusion of ORGN001.

Efficacy analyses will be performed on the Full Analysis Set (FAS), defined as patients with a confirmed diagnosis of MoCD Type A who have no antenatal and/or postnatal brain imaging prior to initiation of treatment with ORGN001 that indicates cortical or subcortical cystic encephalomalacia or clinically significant intracranial hemorrhage.

Additionally, two modified Full Analysis Sets (mFAS) will be used to support the analyses on the FAS:

- Neonate mFAS (NmFAS), [REDACTED]
- Pediatric mFAS (PmFAS) [REDACTED]

Available efficacy data of all patients excluded from the FAS will be displayed in listings and described in narratives.

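### Pooling EAP-entered with treatment-naïve children in the safety tables may understate early reactions on starting ORGN001

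*Combined protocol and SAP*

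**What the plan says.** All references are to the combined protocol and SAP.

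- **Objective (3.1).** The primary objective begins "To evaluate the safety and efficacy of ORGN001 in neonate, infant, and pediatric patients with MoCD Type A who are either treatment-naïve" and goes on to include children who have had compassionate-use ORGN001.
- **Entry (7.2).** Patients may be "previously untreated with ORGN001 or treated with ORGN001 through the EAP". No minimum or maximum prior exposure is stated.
- **Collection of adverse events (13.5.2).** "All serious and nonserious AE information will be collected from the time informed consent is signed until study completion".
- **What is not an adverse event (13.5.1).** The exclusions include "Pre-existing diseases or conditions present or detected prior to the Screening/Baseline evaluation that do not worsen". The same section counts worsening as an adverse event: "Exacerbations of a chronic or intermittent pre-existing condition, including either an increase in frequency and/or intensity of the condition".
- **Treatment-emergent events (14.8.1).** "Treatment-emergent adverse events are AEs with onset on or after the first date of ORGN001 administration". Which dose this means for an EAP entrant is not stated.
- **Population (14.2).** "Safety analyses will be performed on a Safety Set, defined as all patients who received at least 1 infusion of ORGN001". The visible text of 14.8 to 14.8.3 does not separate patients by prior ORGN001 exposure.
- **Prior medication (8.2).** This is "defined as any drug or substance taken by the patient within 28 days prior to the time the parent or legal guardian signs" the consent form, up to the first ORGN001 dose.

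Several paragraphs of 14.8.1, and the definitions of the neonate and pediatric modified analysis sets in 14.2, are redacted.

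**The concern.** A treatment-naïve child is observed from the first exposure to ORGN001. A child who enters from the EAP had that first exposure before adverse-event collection began. Both count equally in the denominator of every treatment-emergent table, but only the naïve child can contribute a first-exposure reaction to the numerator.

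The question a prescriber or regulator will ask of these tables is how often a child who starts ORGN001 has a reaction. If a material share of the Safety Set comes from the EAP, the pooled incidence answers it with a denominator that is too large. Section 14.1 sets no minimum number of patients, so the trial may be small and a few EAP entrants could shift a percentage noticeably.

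**Working it through.** **Step 1. Can an EAP-period reaction reach the tables?** Take a reaction that starts after the first EAP dose and has resolved or is stable by study consent.

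- If the reference date in 14.8.1 is the first EAP dose, the treatment-emergent window opens before collection does. The reaction falls inside the window but is not collected (13.5.2) or, if still present and stable, is not an adverse event (13.5.1).
- If the reference date is the first study dose, the reaction predates the window.

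It is absent on both readings. The readings differ for an event that starts between study consent and the first study dose: it is treatment-emergent on the first reading and not on the second. The ambiguity therefore needs settling, but it is not the source of the dilution. The source is the start of collection combined with pooling.

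**Step 2. Is EAP exposure captured elsewhere?** In part. Prior EAP use is checked at eligibility (7.2) and a complete medical history is taken (4.3.3). The prior-medication window (8.2) covers at most the last 28 days before consent plus the time to the first study dose. If the first ORGN001 dose is read as the EAP dose and was given more than 28 days before consent, the window contains nothing. No field for EAP start date, duration or EAP-period events is visible there or in the exposure summaries (14.5).

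**Step 3. Size.** The plan states no sample size, adverse-event rate or EAP share, so there is no figure to reproduce. Everything below is an illustration on assumed inputs.

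Let *p* be the incidence in naïve children, *f* the EAP share of the Safety Set, and *d* the relative reduction in recorded incidence among EAP entrants. Then:

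pooled incidence = *p* × (1 − *f* × *d*)

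- Early reaction seen only in naïve children (*d* = 1), assumed *N* = 12 and *p* = 30%:
  - 2 EAP entrants: 0.30 × 10/12 = 25%
  - 4 EAP entrants: 0.30 × 8/12 = 20%
  - 6 EAP entrants: 0.30 × 6/12 = 15%
- Milder case (*d* = 0.5, *p* = 30%): 28.5%, 26.3% and 22.5% for *f* = 10%, 25% and 50%.
- No difference between groups (*d* = 0): 30% for any *f*.
- More events recorded in EAP entrants (*d* = −0.5): pooled/naïve ratio 1.05, 1.125 and 1.25 for *f* = 10%, 25% and 50%, which is overstatement.

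**Step 4. Chance of seeing an early reaction at all.** Assume *N* = 10 and a true risk of 20% that only naïve children can show. The chance of at least one event is 1 − 0.8^(number naïve):

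- 10 naïve: 89.3%
- 7 naïve: 79.0%
- 5 naïve: 67.2%

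**Step 5. Reassurance from zero events.** The one-sided 95% upper bound is 1 − 0.05^(1/*n*). For 10 pooled patients it is 25.9%; for 5 naïve patients it is 45.1%. If half of ten patients came from the EAP, the pooled table would suggest a much tighter bound on first-exposure risk than the data support.

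**The case against.** The strongest reply is that a split may already exist: several paragraphs directly above the treatment-emergent definition are redacted. That stands, and the point is therefore confined to the visible text. It is also fair that every study must start collection somewhere, that consent is the natural boundary, and that adverse events after consent will be listed, so a reader could tabulate them by prior exposure if that status is shown. This reduces the severity, but prespecified tables are what will be read and cited.

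A reader might infer several stronger claims that the documents do not support:

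- **That EAP exposure is unrecorded.** It is checked at eligibility and partly captured as prior medication. The gap is incomplete capture.
- **That no reaction beginning in the EAP can be an adverse event.** Section 13.5.1 excludes only those that do not worsen.
- **That the EAP admits only children who tolerated the drug.** Only survival to consent is certain. Section 7.2 does not require tolerated or current treatment, and the contraindication exclusion in 7.3 is a physician's judgement. Section 2.3 reports no withdrawal for an adverse event to date, although it gives no EAP-specific data.
- **That first escalation goes unobserved in EAP entrants.** The synopsis and 9.5 describe dosing from study Day 1 with later adjustment, and no exemption for EAP entrants is visible.

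**Conclusion.** The point holds in a limited form. On the visible text, early or first-exposure reactions that resolved or stayed stable before consent cannot appear in the safety tables for EAP entrants, who still count in the denominator. Pooled treatment-emergent incidence may therefore understate early reactions on starting ORGN001. The size is unknown because the EAP share is not given. The fall from 30% to between 25% and 15% rests on an assumed 12 patients, 2 to 6 EAP entrants, and the extreme case in which EAP children show none of these reactions.

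It would be tempting to conclude that adverse-event rates in general are understated. That is not shown. Many events may be due to the disease rather than the drug, and the pooled rate could move either way (*d* = 0 gives no bias, *d* < 0 gives overstatement). This is an inexpensive reporting improvement, conditional on the redacted text not already providing it.

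**What to change.** 1. In 14.8 to 14.8.2, present treatment-emergent events, serious events and laboratory abnormalities for treatment-naïve and EAP-entered patients separately as well as pooled. State that the naïve column is the one to read for incidence on starting ORGN001.
2. In 14.8.1, state whether the reference date for EAP entrants is the first EAP dose or the first study dose.
3. For enrolled EAP entrants, record the EAP start date and exposure. List EAP-period adverse events from medical history separately, without counting them in rates.

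If the redacted text of 14.8.1 already contains the split, only items 2 and 3 remain, to the extent that they are not covered there too.

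Two further steps are not recommended. Treating every condition that arose after the first EAP dose as emergent on drug would sweep in seizures and progression of the disease itself. Listing EAP children who never enrolled would need data on non-participants who are not covered by this study's consent.

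The cost is one extra table column with small cells, plus a short history entry for EAP entrants. EAP histories will be incomplete, which is why those events should be listed and not used for rates.

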6.1.2. Criteria for Adjustment or Stopping Doses

The following are examples of possible clinical conditions and potential actions to be taken with respect to study drug administration in a given child or group of children. This list is not comprehensive. Consideration of dose changes for each patient will be assessed individually by the treating physician, based on the patient's clinical status and review with the medical monitor.

- Scenario 1: Any study drug-related SAE that results in the death of a single patient

Action: No further dose escalations will take place in any patient; pending evaluation, all other patients will maintain their current dose level and no new patient will be enrolled in the study. A substantial amendment to the Clinical Trial Authorization will be submitted

to the relevant Competent Authorities for approval prior to restarting enrollment and allowing further dose escalations in the event that any study drug-related SAE results in the death of a single patient.

- Scenario 2: One or more study drug-related SAEs in a single patient

Action: If the treating physician, in consultation with the medical monitor, determines that a dose reduction could be expected to reduce the risk of the SAE and not increase the risk of MoCD-related symptoms, the patient may be treated with a lower dose of ORGN001. Subsequent dose escalation for that patient may be considered, based on clinical assessment by the treating physician in consultation with the medical monitor.

- Scenario 3: The same study drug-related SAE occurs in 2 different patients.

Action: In addition to the actions taken under Scenario 2, dosing in subsequent patients may be limited, to achieve concentrations below those observed in the patients with drug-related SAEs, patient to clinical assessment by the treating physician in consultation with the medical monitor.

- Scenario 4: PK exposure in a single patient exceeds the AUC NOAEL limit by greater than 10%

Action: The patient's dose is reduced to a dose level that results in exposure that is below the NOAEL exposure.

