8.3. Treatment Adherence

The Investigator or designee must ensure that the parent or legal guardian of each study patient is adequately informed of the study drug regimen required for compliance with the study protocol. Daily infusions of ORGN001 at home will be administered by the patient's parent or legal guardian with the support, [REDACTED]. If a parent or legal guardian is unable to administer ORGN001 on a given day, study drug may be administered by an alternate caregiver, provided that training for ORGN001 administration by

the alternate caregiver has been documented. Patient adherence to the study drug regimen will be monitored throughout the study by reviewing study drug administration records and study drug accountability. Study drug accountability (including accounting of study drug returns) will be reviewed with the patient's parent or legal guardian at each study visit.

Missed treatments must be clearly documented in the patient's study records and recorded in the CRF. Additionally, these must be documented as protocol deviations.

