13.5.6. Causality Assessment

An Investigator causality assessment must be provided for all AEs. This assessment must be recorded in the CRF and any additional forms, as appropriate. The definitions for the causality assessments are as follows:

- Not related (unrelated): this relationship suggests that there is no causal association between study drug and the reported event.
- Unlikely related: this relationship suggests that the clinical picture is highly consistent with a cause other than the study drug, but attribution cannot be made with absolute certainty, and a relationship between the study drug and AE cannot be excluded with complete confidence.
- Possibly related: this relationship suggests that treatment with study drug may have caused or contributed to the AE, ie, the event follows a reasonable temporal sequence from the time of drug administration, and/or follows a known response pattern to the study drug, but could also have been produced by other factors.
- Probably related: this relationship suggests that a reasonable temporal sequence of the event with study drug administration exists, and the likely causal association of the event with study drug. This will be based upon the known pharmacological action of study drug, known or previously reported adverse reactions to the study drug or class of drugs, or judgment based on the clinical experience of the Investigator.
- Definitely related: temporal relationship to the study drug. Other conditions (concurrent illness, concurrent medication reaction, or progression/expression of disease state) do not appear to explain event, which corresponds with the known pharmaceutical profile, improves with study drug discontinuation, and/or reappears with study drug rechallenge.

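### The causality scale asks only about study drug, so harms of daily IV delivery may be missing from the related-TEAE table and cannot be attributed to delivery in the other tables

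*Combined protocol and SAP*

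**What the plan says.** Four parts of the combined protocol and SAP bear on this.

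- **What counts as an adverse event (13.5.1).** The definition takes in events "temporally associated with the use of a medicinal product or procedure, whether or not considered related to the medicinal product or procedure", and the same section names extravasation as included.
- **How cause is rated (13.5.6).** There are five categories, each worded around study drug. The lowest reads "this relationship suggests that there is no causal association between study drug and the reported event". The middle one reads "this relationship suggests that treatment with study drug may have caused or contributed to the AE".
- **What is tabulated (14.8.1).** "Treatment-emergent adverse events will be summarized by System Organ Class (SOC) and Preferred term for all events", and again for "those considered at least possibly related (including missing relationship) to ORGN001 by the Investigator". Separately, "Serious TEAEs will be tabulated by SOC and Preferred term", with no condition on relationship.
- **What triggers the example actions (6.1.2).** Scenario 1 is "Any study drug-related SAE that results in the death of a single patient". Scenarios 2 and 3 likewise require an SAE related to study drug.

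The Synopsis sets once-daily dosing throughout the study, and Section 4.1 describes 36 months with possible continuation. On home dosing, Section 8.3 says: "Daily infusions of ORGN001 at home will be administered by" the parent or guardian, or a trained alternate caregiver.

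**The concern.** The treatment under evaluation is the drug together with its route. No patient can receive ORGN001 in this trial without repeated venous access. The definition of an adverse event recognises harm from procedures, but the causality question does not. An investigator who answers that question literally can rate an infected or thrombosed line as unrelated, because the molecule did not cause it.

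Two things are at stake. First, the related-TEAE table is likely to be read as the risk attributable to treatment. The protocol already summarises experience in that way: the Synopsis and Section 2.3 report that no serious reaction has been attributed to ORGN001. Second, with no control arm, the all-TEAE table cannot show whether a septic episode came from the line, the disease or ordinary childhood illness. Attribution to delivery is available only if someone records it when the event is reported.

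**Working it through.** The plan gives no adverse event rate, sample size or event count for this point, so there is no figure to reproduce. The check sets the provisions side by side and follows one event through them.

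**Step 1. Does each provision reach an event caused by delivery rather than by the molecule?**

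| Provision | Scope | Reaches a delivery event? |
|---|---|---|
| 13.5.1, definition | product or procedure | Yes |
| 13.5.3, recording | all events, whatever the cause, by diagnosis | Yes |
| 13.5.6, not or unlikely related | study drug against another cause | These are the ratings a literal reader would give |
| 13.5.6, possibly related | treatment with study drug | Arguable; could be read to include the infusion |
| 13.5.6, probably related | known pharmacology, known reactions, or investigator's judgment | Only through judgment |
| 13.5.6, definitely related | fit with the drug's known profile | Poor fit |
| 14.8.1, all TEAEs | no relationship filter | Yes |
| 14.8.1, serious TEAEs | no relationship filter | Yes |
| 14.8.1, related TEAEs | at least possibly related to ORGN001, or missing | Depends on the rating |
| 6.1.2, Scenarios 1 to 3 | SAE related to study drug | Depends on the rating |

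**Step 2. Follow one delivery event by its rating.**

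- Left blank: it enters the related table, because missing counts as related.
- Rated possibly related or higher: it enters the related table, but as an ORGN001 event with no mark that delivery was the cause.
- Rated not or unlikely related: it is absent from the related table and outside the wording of Scenarios 1 to 3, but present in the all-TEAE table and, if serious, in the serious-TEAE table.

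**Step 3. Express the loss.** Let D be the number of delivery-caused TEAEs and s the share rated not or unlikely related.

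- Missing from the related table: s × D. At s = 0 this is 0; at s = 100% it is D.
- Missing from the all-TEAE table: 0 × D = 0 at every s. The same holds for serious events in the serious-TEAE table.

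The documents give neither D nor s, so s is left at its full range of 0 to 100%.

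**Step 4. What does not depend on s.** Delivery events rated unrelated sit among disease and background events. Those rated related sit among drug effects. Either way the visible plan has no field that separates them, unless the recorded diagnosis itself names the line or the infusion.

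**Step 5. Is the question asked elsewhere?** The list of SAE report contents in 13.5.8 asks for causality without mentioning delivery. Section 8.2 asks for documentation of events related to certain therapies and procedures, but in context these are concomitant ones. It adds no causality category and no table for the ORGN001 infusion.

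**The case against.** A reader might infer that delivery harms disappear from the safety report, or that the plan understates the risk of treatment. The documents do not support either. Every adverse event is recorded whatever its cause and by diagnosis (13.5.3). All TEAEs are tabulated overall and by severity, in patients and in events, and serious TEAEs are tabulated unfiltered (14.8.1). The DMC has access to all safety data (6.2). Study or site termination for a serious or unacceptable risk does not depend on drug-relatedness (6.1.3). At most, one subset table is narrower than the benefit-risk question needs. That subset also matches the stated safety endpoint, which is relationship to study drug (3.2).

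Nor is misrating certain. The wording of the middle category can be read to include the infusion, and blank ratings count as related. This stands, but it does not close the gap. If some investigators read the category broadly and others narrowly, the related table mixes two definitions, and a completed rating of unrelated is not rescued by the rule for blanks.

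Several lines of 14.8.1 and parts of the home-infusion text in 8.3 and 9.5 are redacted, so a further summary may exist there. That limits the claim to the visible text. The causality definitions in 13.5.6 show no redaction, however, and they supply the data that any such summary would use.

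The scenario point is the weaker half. Section 6.1.2 offers its list as examples and says it is incomplete. Scenarios 2 and 3 act through dose or concentration, for which drug-only wording may be deliberate. What stands is that the text does not say which meaning is intended.

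A reader might also want to size the problem from a catheter infection rate. The visible text gives no such rate, names no access device for dosing, and sets no sample size, so that figure would rest entirely on assumption.

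**Conclusion.** The concern holds as an attribution gap. On the visible text, cause is asked only in relation to study drug, although the adverse event definition covers procedures and treatment is a daily infusion. Delivery events may be missing from the related-TEAE table and from the wording of Scenarios 1 to 3. They remain in the all-TEAE and serious-TEAE tables, where nothing records that delivery caused them and no comparator can show an excess.

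The share of delivery events lost from the related table is unknown, from 0 to 100%. The loss from the all-TEAE and serious-TEAE tables is nil. The conclusion assumes that the CRF holds no delivery item beyond those described in the protocol, and that the redacted text does not supply one. This is a cheap improvement to reporting, not a defect that invalidates the safety analysis.

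**What to change.** 1. Add one item to the adverse event CRF and one line to 13.5.6: *related to IV access, infusion procedure or device: yes/no*, rated separately from relationship to study drug.
2. In 14.8.1, tabulate TEAEs and serious TEAEs related to *ORGN001 or its administration* beside the drug-only related table, so that both readings are reported.
3. Reconcile 13.5.1, 13.5.6 and 6.1.2 by stating whether study drug-related includes administration-related events. The choice belongs to the sponsor; no dosing, enrolment or stopping rule is proposed here.

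The cost is one field, one extra table and a clarifying sentence. The downside is a higher stated related-event rate than the drug-only table would show. The new item is also an investigator's judgment and does not replace a comparator; it only makes the attribution explicit.
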